## **7.0 Reporting of Adverse Events or Unanticipated Problems involving Risk to Participants or Others**

Participants could react adversely during the assessment and/or intervention procedures or symptoms could worsen during the course of the study (although this worsening may or may not be related to the treatment). Once weekly during the eight-week MBCT or MBSR intervention, participants will complete a brief medication questionnaire, the Beck Depression Inventory-II, and the Spielberger State-Trait Anxiety Inventory. The PI and study coordinator will examine weekly medication status and symptom scores with the appointed study medical monitor ([name], JD, MSN, PMHNP-BC) and note changes. If we see evidence of substantial worsening, at-risk participants will be removed from the study and appropriate safety measures will be taken. Dropout rates will be examined at least quarterly, depending on enrollment. If there are concerns about attrition, the research team will review information regarding each participant who withdrew and study procedures, and ensure adequate subject protection and data integrity.

Reporting of adverse events will occur as follows:

During the study, if patients become unstable, [name], the Psychiatric mental health nurse practitioner, will be monitoring clinical change and risk of suicidality.

Any serious adverse event (e.g., death, suicide attempt, hospitalization) will be reported by telephone within 24 hours to the IRB and the DSMB. A full written report of the event will be sent to these entities within 24 hours of the event's occurrence.

Any moderate adverse event (e.g., causing interference with usual activities or requiring treatment) and which appears definitely, probably, or possibly related to study participation will be reported to the IRB and DSMB in writing within seven working days. Any mild adverse event will be summarized in the IRB annual progress reports.

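### Section 7.0 gives a moderate adverse event judged unrelated no route to the IRB or DSMB, gives mild events no route to the DSMB, and dates the serious-event written report from occurrence rather than awareness

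*Combined protocol and SAP*

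**What the plan says.** Section 7.0 of the protocol sets three tiers.

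- **Serious.** Such an event "will be reported by telephone within 24 hours to the IRB and the DSMB", with no condition on cause. In addition, "A full written report of the event will be sent to these entities within 24 hours of the event's occurrence".
- **Moderate.** The tier opens "Any moderate adverse event (e.g., causing interference with usual activities or requiring treatment" and then limits the duty to an event "which appears definitely, probably, or possibly related to study participation will be reported to the IRB and DSMB in writing within seven working days".
- **Mild.** "Any mild adverse event will be summarized in the IRB annual progress reports". There is no condition on cause, and the DSMB is not named.

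The same section allows that "symptoms could worsen during the course of the study (although this worsening may or may not be related to the treatment". Its scheduled safety collection is weekly: "Once weekly during the eight-week MBCT or MBSR intervention, participants will complete a brief medication questionnaire, the Beck Depression Inventory-II", together with the state-trait anxiety inventory. For review, "The PI and study coordinator will examine weekly medication status and symptom scores with the appointed study medical monitor". Section 6.0 (Risks) lists clinical worsening among the risks of the eight-week intervention.

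**The concern.** Relatedness is a filter on the middle tier only. An event bad enough to disrupt normal activity or need treatment can go unreported because it was attributed to the underlying illness, while a lesser event with the same attribution is at least summarised for the IRB.

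The gap falls on the harm this study is most likely to meet. Participants in the clinical arms are selected for depression, anxiety or stress, so the existing condition is always a plausible explanation for worsening. Section 3.0 requires them to be already registered for MBCT or MBSR, and no untreated group is described against which a background rate could be judged. Section 7.0 does not say who judges relatedness. What the IRB and DSMB receive for moderate worsening therefore depends on case-by-case attribution.

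The second matter is timing. A deadline that runs from the event, not from knowledge of it, can expire before anyone in the study could act on it. What is at stake there is compliance with the rule, not whether the event is reported.

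**Working it through.** There is no stated statistical figure to reproduce. Two checks apply.

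**1. Severity by relatedness, from the rules in Section 7.0.** Here, related means at least possibly related.

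| Severity | Judged | IRB | DSMB |
|---|---|---|---|
| Serious | related | 24 h | 24 h |
| Serious | unrelated | 24 h | 24 h |
| Moderate | related | 7 working days | 7 working days |
| Moderate | unrelated | none | none |
| Mild | related | annual | none |
| Mild | unrelated | annual | none |

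The IRB has no route in 1 of 6 cells and the DSMB has none in 3 of 6. The scale is inverted for the IRB only: the unrelated mild event is summarised and the unrelated moderate one is not. For the DSMB both are absent.

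Other sections do not fill the empty cells. The weekly score review and the dropout review in Section 7.0 are carried out within the study team, and neither is said to go to the IRB or DSMB. Section 8.0 ends participation when psychopathology calls for a medication change. Such an event fits the moderate description, since treatment was needed. If it were judged unrelated, the participant would leave with no report under the stated rules.

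**2. The serious-event clocks.** The written report is due 24 hours after occurrence. The telephone report is due in 24 hours from a point that is not stated. As an example, take an event first learned of at a weekly contact 72 hours later. The written deadline passed 72 − 24 = 48 hours before staff knew.

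How often this happens cannot be read from the documents. To show the range, assume that event times are uniform over a 168-hour week, that a share *s* of serious events becomes known at once by some other route, and that the rest become known only at one weekly contact. Then

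P(known within 24 h) = *s* + (1 − *s*) × 24/168.

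| *s* (assumed) | Known within 24 h |
|---|---|
| 0 | 14.3% |
| 25% | 35.7% |
| 50% | 57.1% |
| 75% | 78.6% |
| 90% | 91.4% |

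The result crosses one half where *s* + (1 − *s*)/7 = 0.5, that is at *s* = 5/12, about 42%. The documents give no value for *s*, so they do not settle whether most deadlines would be met. They establish only that the deadline can lapse before awareness.

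**The case against.** The strongest reply is that worsening is well watched and the gap is narrow. The filter removes only events thought not even possibly related, a low bar for worsening during an MBI. Hospitalisation and suicide attempts count as serious and are reported whatever the cause. Scores and medication status are reviewed weekly with a medical monitor, and dropout is examined at least quarterly. All of this stands. It defeats the stronger inference that the IRB and DSMB could not detect an excess of worsening at all. It does not give the excluded moderate events a route, because those reviews stay inside the team.

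On timing, a reader might infer that about 6 in 7 serious events (86%) would miss the written deadline. That needs *s* = 0, with the weekly form as the sole source of knowledge. The documents do not say so. They describe weekly classes, telephone support from facilitators if needed, instructors who may identify suicidality, and an automatic alert on the suicidality item of the depression inventory. None is a scheduled daily adverse-event check: the alert depends on a completed inventory, and the daily survey is described as covering home practice only. But they rule out treating 86% as a finding. The weekly forms are not described as adverse-event forms either.

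A reader might also infer that the clock leaves the serious-event record incomplete. It does not, since a late report is still a report. Nor does the telephone deadline run from occurrence; its start is simply not given.

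The suicide safety plan mentioned in Sections 4.0 and 6.0 is not in the text available here and may contain notification rules for suicidality.

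**Conclusion.** The concern holds as a gap in the reporting rules. Under Section 7.0 as written, a moderate event judged unrelated goes to neither oversight body, and mild events do not go to the DSMB. This follows from the wording alone. Its consequence is that part of the moderate worsening can be missing from what the IRB and DSMB see. How many events that would be cannot be estimated, because the documents give neither event rates nor the share likely to be judged unrelated.

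The written-report deadline can expire before staff are aware, and the telephone deadline is undefined at its start. These cause avoidable deviations of unknown frequency.

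A contrast of 0% of unrelated moderate events against 100% of mild events is tempting, but it is true for the IRB only. No endpoint, sample size or analysis is affected; the matter is safety oversight.

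**What to change.** Amend Section 7.0 in two places.

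1. List in the annual summary, alongside the mild events, every moderate event that the seven-day report does not cover, regardless of its judged relatedness. Send that summary to the DSMB as well as the IRB. Every cell of the grid then has a route to both bodies.
2. State that both serious-event clocks, telephone and written, start when study staff or an MBI instructor first become aware of the event.

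The cost is a few sentences and a slightly longer annual table, which will list more background events. No visits, staff or treatment rules change.

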## 8.0 Study Withdrawal/Discontinuation

### **Criteria for study termination**

Patients will be terminated from the study if they meet the following criteria:

- 1) Patient exhibits psychopathology requiring changes in medication dosage or type
- 2) Patient requires inpatient hospitalization or medication
- 3) Patient becomes medically unstable and necessitates intensive medical intervention as determined by the patient's physician
- 4) Patient becomes suicidal as determined by MBI instructors and requires inpatient hospitalization or more intensive treatment
- 5) Patient misses more than 50% of MBI sessions (determined to be an adequate dose)(Crane and Williams 2010).

Patients terminated because of exacerbation of symptoms will be considered treatment non-responders, whereas patients terminated due to medical problems or suicidality may participate again once they are medically and psychologically stable. They will be enrolled in a subsequent group at a later time.

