### **3.0 Inclusion/Exclusion Criteria**

Eligibility Criteria for Pre-Study Paradigm Testing:

- Before commencing the research delineated in this protocol, we will collect EEG and fMRI data from 30 healthy subjects to test all of our experimental paradigms and make sure they are working properly.
- Flyers and ResearchMatch will be used to circulate information about the study to the Vanderbilt campus and surrounding community.
- The subjects must be between the ages of 18 and 55.
- The 30 subjects will not complete the full pre-screening questionnaire, but will receive a phone screen to make sure they can safely participate in the EEG and fMRI protocol.

Eligibility Criteria Across All Study Arms:

- At prescreen, must be currently registered for MBCT or MBSR; at posttest, must have attended five of eight sessions for “completion”.
- Must possess English language skills sufficient for providing informed consent, completing questionnaires, and understanding instructions
- Age range: 18-55

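### Participants who worsen, change medication or attend too few sessions leave the study itself, so continuous pre/post estimates, chiefly DASS-A, describe only those who stayed

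*Combined protocol and SAP*

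**What the plan says.** Section numbers below are those of the body headings in the combined protocol and SAP.

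- **Section 8.0, Criteria for study termination.** "Patients will be terminated from the study if they meet the following criteria". The list includes "Patient exhibits psychopathology requiring changes in medication dosage or type" and "Patient misses more than 50% of MBI sessions".
- **Section 7.0.** "If we see evidence of substantial worsening, at-risk participants will be removed from the study".
- **Section 3.0, criteria for all arms.** Attendance at five of the eight sessions, judged at post-test, appears among the eligibility criteria.
- **What happens to those terminated (Section 8.0).** "Patients terminated because of exacerbation of symptoms will be considered treatment non-responders". Those terminated for medical problems or suicidality "may participate again once they are medically and psychologically stable", in a later group. Nothing is said about low attenders.
- **Section 5.0.** DASS-A is the primary anxiety measure, and the DASS is listed for pre-test, post-test and follow-up. BDI-II and STAI are taken at screening, weekly and at post-test. Medication changes are also recorded weekly.
- **Section 9.0.** It gives power calculations and one sentence on a repeated-measures ANCOVA of the fMRI data. It names no analysis set and no method for missing post-tests. The only attrition figure is the 18% allowance in the Anxiety Arm.

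**The concern.** The triggers end participation in the study, so they end data collection as well as the course. Worsening and a need for more medication are close to what DASS-A, BDI-II and STAI measure, and low attendance may be related to it. If these people have no post-test, mean change is averaged over a group selected partly on how they fared. No untreated comparison group is described in which the same selection could cancel. (The fMRI power paragraph mentions a PE group, but no section describes one.)

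Section 1.0 says the pilot is meant to refine hypotheses for larger grant proposals and to help identify who does and does not benefit. An unlabelled completer effect could be carried forward as the effect in everyone enrolled, and losing those who worsened narrows the range of outcomes from which non-benefit could be studied.

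**Working it through.** **1. Who has a post-test if the rules are followed as written.**

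- *Low attenders (three or fewer of eight):* terminated, with no post-test and no outcome rule.
- *Exacerbations:* terminated and labelled non-responders. The label can enter a response analysis such as Aim 4, but response is not defined and the label gives no value for a continuous measure.
- *Medical problems or suicidality:* may re-enrol. That yields a post-test after a new course, and no rule says which course counts.
- *Medication change:* terminated. Unless it is classed as an exacerbation, no outcome rule applies.

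BDI-II and STAI have weekly scores up to removal. DASS-A, ERP and BOLD have no weekly values. The go/no-go power calculation assumes four assessment points, but no schedule places them and nothing collects them after termination.

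**2. The plan's own attrition figure.** Anxiety Arm: 34 needed, 18% attrition. 34 / (1 − 0.18) = 41.46, rounded up to 42, which matches the plan. This protects the number who stay. It does nothing about who they are.

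**3. Illustration of the size.** Let q be the fraction lost to these removals and r the mean change in those lost divided by the mean change in those who stay. The all-enrolled change is (1 − q) + q·r times the stayers' change, so

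overstatement = 1 / ((1 − q) + q·r) − 1.

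The 18% is the plan's figure. The share of it due to these removals, and r, are assumptions. The second row lets half of the attrition be such removals and the rest change like those who stay.

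| | r = 1 | r = 0.5 | r = 0 | r = −0.5 |
|---|---|---|---|---|
| q = 0.18 | 0% | 1/0.91 − 1 = 9.9% | 1/0.82 − 1 = 22.0% | 1/0.73 − 1 = 37.0% |
| q = 0.09 | 0% | 1/0.955 − 1 = 4.7% | 1/0.91 − 1 = 9.9% | 1/0.865 − 1 = 15.6% |

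Negative r is possible because worsening is itself a trigger.

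**4. A second illustration, with no true effect.** Assume mean change 0 and SD 1, with the 18% at the unfavourable end of a removal score lost, where that score correlates ρ with change. Apparent improvement among those kept is ρ·φ(z)/(1 − q), with z = 0.915 and φ(z) = 0.2625, so ρ × 0.2625/0.82 = ρ × 0.32. That is 0.10 SD at ρ = 0.3, 0.16 SD at 0.5 and 0.32 SD at 1.0. In 20,000 simulated trials with 34 of 42 kept, a two-sided 5% paired test rejected in about 9%, 17% and 64% of runs respectively, and in 4.9% when removal was unrelated to change.

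**5. Cost of post-testing.** Anxiety Arm: 42 − 34 = 8 people. DASS 10 min + BDI-II 5–10 + STAI 5–10 = 20–30 min each, so 160–240 min, or 2.7–4.0 hours. If 18% held in all arms (assumption; the others state no figure): 42 + 26 + 30 = 98, 0.18 × 98 = 17.6, about 18 people, 360–540 min, or 6–9 hours.

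**The case against.** The case for the plan has substance.

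- **A reader might infer that ERP, BOLD and go/no-go are biased in the same way.** The documents do not show this. The triggers are symptoms, medication and attendance, and Aim 4 treats the relation between P1 markers and treatment response as an open question. These results come from those who stayed, but a bias toward benefit in them is an assumption.
- **A reader might infer that removed patients disappear from every analysis.** They do not. Those removed for exacerbation count as non-responders, which is unfavourable to the intervention. The point is limited to continuous outcomes.
- **The medication rule protects interpretation.** Entry requires a stable regimen, and in a pre/post design scores after escalation may credit drug benefit to the course. An all-enrolled analysis can therefore also err toward benefit. This stands and changes the fix.
- **The removal text is softer than it first looks.** Section 6.0 answers substantial worsening with referral to care, and Section 7.0 removes those at risk. Section 7.0 also has dropout examined at least quarterly, with withdrawals reviewed if attrition is a concern. That leaves some doubt about how many would be removed, but none of it is an analysis rule or obtains a post-test.
- **A reader might see a contradiction at four of eight sessions,** which is neither terminated nor complete. The two thresholds can serve different purposes: such a person stays in the study as a non-completer.
- **This is an exploratory mechanism pilot.** Section 8.0 describes its attendance threshold as "determined to be an adequate dose", and an adequate-dose estimate is a defensible target. The plan does not say that this is what it estimates.

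**Conclusion.** The point holds for continuous pre/post outcomes. The removal rules take people out of data collection, nothing replaces their post-test, and the resulting estimates describe those who stayed. For DASS-A an outcome-related selection toward benefit is plausible. BDI-II and STAI are less exposed because weekly scores exist up to removal, although the plan does not say they will be used.

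The size is unknown. The 0–37% range is conditional, not an estimate. Its upper end needs all of the 18% to be such removals and the lost group to worsen, on average, by half the improvement of those who stay. If those lost change like those who stay, the bias is zero. It would be wrong to read this as showing that the trial's effects are overstated by any given amount, or that a completer analysis is invalid. The defect is that the selected estimate is not declared and that an inexpensive remedy for the self-reports is left unused. This should be changed, but it does not undermine the pilot.

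**What to change.** (a) In Sections 7.0 and 8.0 keep every clinical trigger, but make its consequence stopping the course and laboratory testing. Invite all enrolled participants, where safe and consented, to the scheduled post-test DASS, BDI-II and STAI.

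(b) In Section 9.0 report self-reported outcomes in all enrolled beside the completer analysis. A mixed model can use the weekly BDI-II and STAI. For DASS-A the gain rests on obtaining the post-tests, since someone with a baseline alone tells the model almost nothing about change. Give equal prominence to an analysis that sets aside scores after a medication change, using the weekly medication check-in. Count each re-enrolled person once, under the first enrolment, and report the second course separately.

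(c) Move the five-of-eight rule out of eligibility and into the definition of the completer set, leaving the number as it is. Label ERP, BOLD and go/no-go results as completer estimates.

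The cost is a protocol amendment, with consent wording changed only if it does not already allow this (the consent pages were not available), and about 2.7–4.0 participant-hours in the Anxiety Arm, or 6–9 hours across arms if 18% applied throughout. Self-reports are already held in REDCap. People who decline all contact stay missing, and the mixed model then relies on a missing-at-random assumption. The all-enrolled estimate may be smaller, and its power cannot be stated because the plan gives no effect size for the self-reports.

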## 9.0 Statistical Considerations

**Power analysis.** Presently, no studies have explored P1 ERP activity in anxious populations before and after an MBCT intervention, so no direct estimation of effect size is available. However, Schoenberg et al. conducted a study in which ADHD-related ERP markers were monitored before and after an MBCT intervention. Therefore, mean amplitude differences and standard deviations from the study were used to determine the sample size for the proposed research. An a priori power analysis conducted using PASS version 11 software indicated that a minimum of 34 patients are needed to reject the null hypothesis with 80% power at a type I error rate of 0.05. Accounting for 18% attrition, 42 patients will be recruited in total for the Anxiety Arm.

A repeated-measure ANCOVA of pre- and post-treatment fMRI data will be performed to quantify the MBCT group and test Hypothesis 1(a) [*Target engagement will be identified through a significant interaction (post vs. pre-intervention; negative vs. neutral words; NoGo vs. Go) involving critical nodes of the fronto-parietal control network (dACC, FPC, AI) and decreased activation in limbic regions (hippocampus, amygdala)*]. A classical fixed sample trial design was conducted to determine a sample size that provides a Type I error of no more than 5% and a statistical power of no less than 80%. Based on the pre- and post-treatment fMRI brain imaging data of 10 borderline personality disorder patients for a design of 2 time points and 1 key condition contrast  $[(\text{Negative vs Neutral}) \times (\text{No-Go vs Go})]$  undergoing the same Go-NoGo Emotional Word paradigm we are using in this study) with the differential BOLD response **effect size at 1.963, and 0.274 for the 2 time points** observed in the right amygdala region (ROI with relatively small effect size), a sample size of no less than 25 (21 for a statistical power of no less

**than 80%)** is needed for each group if the BOLD response reduction in PE group is no more than 40%. The above analysis was performed using the PASS version 11 (NCSS Statistical Software, Kaysville, UT). Random effects models employed in the proposed fMRI study have demonstrated to require a sample of 15 – 20 subjects per group to attain sufficient statistical power to detect a relatively small effect size.(Lazar 2008) We have repeatedly demonstrated employing longitudinal-based within(Butler, Pan et al. 2007) and between(Perez, Pan et al. 2015) groups designs that sample sizes  $\geq 15$  (per group) can identify the neural mechanisms supporting treatment-related outcomes. The proposed sample size (n=26) will be recruited for the Depression Arm.

Power analyses for behavioral testing only were estimated using G\*Power software.(Faul, Erdfelder et al. 2009) Effect estimate (0.62) was based on previous use of the go/no-go testing pre/post-mindfulness training.(Loucks 2017) We performed the power calculation with 4 assessment points, and alpha=0.05. The proposed sample size (n=30) for the high stress/chronic pain Arm is sufficient to result in power of 0.80 with an effect size of 0.62.

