## Contemplative Neuroscience & Integrative Medicine Laboratory

- If currently taking maintenance anti-depressant and/or anti-anxiety medication, must have a "stable" regimen as indexed by no medication or dosage changes within the past month
- No prior diagnosis of bipolar I, bipolar II, psychotic personality disorder, borderline personality disorder, and/or narcissistic personality disorder
- No current history ( $\leq 6$  months) of substance abuse/dependence
- No current history ( $\leq 6$  months) of regular meditation practice ( $>1$  session/week;  $>10$  min/session)
- No history of medical illness associated with possible changes in cerebral tissue or cerebrovasculature (e.g., stroke) or with neurologic abnormality (e.g., seizure disorder, cerebrovascular or neoplastic lesion, neurodegenerative disorder, or significant head trauma, defined by loss of consciousness of  $\geq 5$  minutes)
- No current suicidal ideation

*Depression Arm (consists of fMRI scan, EEG with behavior, and self-report measures at pre- and post-treatment testing)*

- Beck Depression Inventory-II (BDI-II) score  $\geq 14$  (an indicator of depressive symptoms of mild to high severity)
- No fMRI contraindications: pregnancy, claustrophobia, or presence of a ferromagnetic object, including orthodontic braces

*Anxiety Arm (consists of EEG with behavior, fMRI scan, self-report measures at pretest and posttest)*

- Diagnosed (via SCID-V Screener) with an anxiety disorder (i.e., generalized anxiety disorder, panic disorder, specific phobia)
- Score of  $\geq 40$  on the Trait subscale of the Spielberger State-Trait Anxiety Inventory (an indicator of anxious symptoms of moderate to high severity)

*Stress Arm*

- Moderate to high stress is necessary for inclusion on behavioral testing/self-report
- Scores on PSS pre-screen  $> 14$  would be considered moderate to high perceived stress.

*Blood Draws (consists of a 10-mL draw at pre-treatment baseline and post-treatment testing; optional for depression/anxiety arm participants)*

Eligibility Criteria:

- At least 110 pounds
- Generally healthy by self-report on day of collection (i.e., free of cold and flu symptoms on the day of collection, no infections within two weeks prior to collection, no known sickle cell disease)
- Including the study draw, blood donation for clinical or research purposes within the preceding eight weeks will not exceed 550 mL
- No more than one blood draw will have occurred during the preceding week

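### The Depression Arm fMRI power figure is for a two-group comparison with an undefined PE group, but the planned test is a single-group pre/post contrast

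*Combined protocol and SAP*

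**What the plan says.** All of the fMRI planning is in section 9.0, Statistical Considerations.

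- **Analysis:** "A repeated-measure ANCOVA of pre- and post-treatment fMRI data will be performed to quantify the MBCT group" and to test Hypothesis 1(a). The target is an interaction of three factors ("post vs. pre-intervention; negative vs. neutral words; NoGo vs. Go"). All three are within-person.
- **Planning data:** "pre- and post-treatment fMRI brain imaging data of 10 borderline personality disorder patients", with right-amygdala "effect size at 1.963, and 0.274 for the 2 time points".
- **Sample size:** "a sample size of no less than 25 (21 for a statistical power of no less" than 80%), and this number "is needed for each group if the BOLD response reduction in PE group is no more than 40" per cent.
- **Recruitment:** "The proposed sample size (n=26) will be recruited for the Depression Arm".

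Section 3.0 (criteria across all study arms) admits people already registered for MBCT or MBSR. It also requires "No prior diagnosis of bipolar I, bipolar II, psychotic personality disorder, borderline personality disorder, and/or narcissistic personality disorder".

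**The concern.** The calculation and the test do not belong to the same design. The calculation has at least two groups, one of them called PE, and a requirement per group. The test has one group and no between-group factor.

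The abbreviation PE is not expanded, and no such group appears elsewhere in the supplied text. Aim 1 in section 2.0 names no comparator. Aim 6 compares treatment types, but on clinical outcomes. Section 4.0 is headed Enrollment/Randomization yet describes no allocation. The caption of Figure 1 names no such group; the figure itself, the schema, the front pages and the appendices were not available.

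A reader will attach the 80% to Hypothesis 1(a). It does not apply there, and the plan gives no power or detectable effect for the contrast that will be tested. The abstract says the pilot is meant to support larger grant proposals, so the wrong figure could be carried forward.

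**Working it through.** **Inputs from section 9.0.** Effect sizes 1.963 (pre) and 0.274 (post); PE reduction of at most 40%; type I error 5%; power 80%; 25 or 21 per group; 26 recruited.

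**Assumptions, because the plan is silent.** Two-sided test; effect sizes in units of the cross-sectional SD (SD = 1); pre/post correlation ρ taken as 0 or 0.5. The planned contrast has one degree of freedom within person, so a paired t-test represents it.

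**1. Reproducing the plan's figure as a two-group comparison**

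- MBCT change: 1.963 − 0.274 = 1.689
- PE change: 0.40 × 1.963 = 0.785
- Difference: 1.689 − 0.785 = 0.904

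Two-sample t-test, d = 0.904, SD 1:

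| n per group | Power |
|---|---|
| 13 | 0.599 |
| 20 | 0.795 |
| 21 | 0.815 |
| 25 | 0.879 |

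The first size to reach 80% is 21, as stated. The figure of 25 is not explained: 90% power would need 27. The match is an inference and depends on SD = 1; with an SD of √2, 40 per group would be needed.

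**2. Can a single-group test give 21 or 25?**

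Paired t-test on a change of 1.689, for 80% power: 5 patients if the SD of change is 1, 8 if it is √2, and 14 if it is 2 (the largest possible value when each time point has SD 1). For 90% power: 6, 10 and 17. None gives 21 or 25.

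**3. What the per-group figure implies**

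- Total: 2 × 21 = 42, or 2 × 25 = 50
- Beyond the 26 recruited: 42 − 26 = 16, or 50 − 26 = 24
- If 26 were split 13 and 13: power about 0.60 under step 1

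**4. The planned test**

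SD of change = √(2(1 − ρ)), so dz = 1.689/1.414 = 1.194 at ρ = 0 and 1.689/1 = 1.689 at ρ = 0.5. The row for 15 is illustrative; it is the per-group size that section 9.0 cites from experience.

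| Analysed | Power, full change, ρ = 0 | Detectable dz at 80% | Share of 1.689, ρ = 0 | Share of 1.689, ρ = 0.5 |
|---|---|---|---|---|
| 26 | >0.99 | 0.57 | 48% | 34% |
| 21 | >0.99 | 0.64 | 54% | 38% |
| 15 | 0.99 | 0.78 | 65% | 46% |

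The share is dz × SD of change ÷ 1.689; for 26 at ρ = 0, 0.572 × 1.414 / 1.689 = 0.48.

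If the true change is half the planning value (1.689/2 = 0.8445), power at ρ = 0 is 0.83 with 26 and 0.74 with 21. At ρ = 0.5 it is 0.99 and 0.96.

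**The case against.** The best defence is that little follows from the slip. The planned test is very well powered on the plan's own effect sizes: even at the largest possible SD of change (2), power with 26 is 0.985. The study is a pilot, nobody proposes to split the 26, and 26 exceeds the per-group minimum of 25. Section 9.0 also supports its size with a rule of 15 to 20 per group and with the team's experience of within-group designs at 15 or more.

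Most of this stands as a limit on the consequence. It does not remove the mismatch. The rule of thumb is not a calculation for Hypothesis 1(a), and section 9.0 does make a formal claim of 5% error and 80% power. The reassurance of power above 0.99 rests on a very large change seen in 10 patients with borderline personality disorder. Borrowing from that group is disclosed and justified by the shared task paradigm, so it is a limitation and not a contradiction, but it is a reason to state the detectable effect.

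Two further points are fair. The figures here are for one region without adjustment, as was the sponsor's right-amygdala calculation, while Hypothesis 1(a) names five regions. A Bonferroni split over five (alpha 0.05/5 = 0.01, my assumption) raises the detectable dz to 0.72 with 26, 0.81 with 21 and 1.00 with 15. Also, the number analysed may not be far from 26: section 3.0 makes scanning part of the Depression Arm, and section 5.0 expects depressed participants to be mainly in MBCT. It still need not be 26, because MBSR registrants are eligible and 18% attrition is allowed for in the Anxiety Arm only.

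**Conclusion.** The concern holds. The only formal fMRI sample size is for a two-group comparison that the described design does not contain. Its requirement is 42 to 50 patients in total, against one arm of 26. This rests on the wording alone; the reproduction of 21 per group supports it but depends on SD = 1 and a two-sided test.

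This is a mismatch between calculation and design, not evidence that the planned test is underpowered. For a single region, unadjusted, the planned test has 80% power for a within-person change of 0.57 SD of change with 26 analysed. If effect sizes are in cross-sectional SD units, that is about a third (ρ = 0.5) to a half (ρ = 0) of the planning change. It should be fixed; confidence is high.

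**What to change.** Delete the sentence about each group and the PE group, and state the figure for the contrast that will be tested. Suggested wording:

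> For a single right-amygdala region, two-sided 5%, without multiplicity adjustment, the study has 80% power for a standardised within-person pre/post change of dz = 0.57 with 26 MBCT participants analysed at both scans, 0.64 with 21, or 0.78 with 15. The result is a within-person change without a comparator. The planning effect sizes come from patients with a diagnosis that this study excludes.

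If several regions will be tested with adjustment, give the detectable change at the adjusted level instead. It would help to add the SD of change or the pre/post correlation from the 10-patient data, the attrition assumed and how 26 was derived, and the number expected to have MBCT and both scans.

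**Cost.** A change of protocol wording, some figures from data the sponsor already cites, and no extra patients. The plan gives up the claim of 80% power against a comparator.

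**If a comparator is intended,** define it, add it to the design and state its power. That means 42 to 50 patients (16 to 24 more), or accepting about 0.60 with 13 per group under the reconstruction above.
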